**Table 8-1 Censoring Conventions for PFS**

Situation	Date of Progression or Censoring	Outcome
Disease progression, and time interval between progression date and previous tumor assessment date with progression-free response is less than or equal to 98 days	Earliest of: 

• Date of first tumor assessment showing new lesion

• Date of first tumor assessment with overall response of PD

	Event
Disease progression, and time interval between the progression date and the previous tumor assessment date with progression-free response is greater than 98 days.	Latest of: 

• the last progression-free assessment date

• randomization date

	Censored
Death without any post-baseline radiological assessment, and time interval between death	Death date	Event

date and randomization date is less than or equal to 98 days		
Death without any post-baseline radiological assessment, and time interval between death date and randomization date is greater than 98 days	Randomization date	Censored
Death before documented progression, and time interval between death date and previous tumor assessment date with progression-free response is less than or equal to 98 days	Death date	Event
Death before documented progression, and time interval between death date and previous tumor assessment date with progression-free response is greater than 98 days	The last progression-free assessment date	Censored
No death or disease progression, no treatment discontinuation due to symptomatic deterioration, and no subsequent anti-cancer therapy (i.e., systemic anti-cancer therapy, anti-cancer surgery, curative radiotherapy).	Latest of 
 
• the last progression-free assessment date
 
• randomization date
 
	Censored
Subsequent anti-cancer treatment (i.e., systemic anti-cancer therapy, anti-cancer surgery, radiotherapy) started prior to progression	Latest of 
 
• the last progression-free assessment date prior to start of anti-cancer treatment
 
• randomization date
 
	Censored
Treatment discontinuation due to symptomatic deterioration prior to disease progression	Latest of 
 
• the last progression-free assessment date before treatment discontinuation date
 
• randomization date
 
	Censored

An adequate disease assessment is a schedule or unscheduled assessment where the overall tumor assessment as assessed by blinded central reviewers is not missing and not unevaluable.

Progression-free survival is calculated as follows.

PFS = Analysis date defined above – randomization date + 1

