The visit window for Day 63 is +/- 7 days of the scheduled visit. Day 63 procedures should be performed in the following order:

- Blood sample for hematology and serum chemistry;
- Blood sample for humoral immunology;
- Weight, and vital signs (blood pressure, temperature and heart rate);
- Urine pregnancy test (female);
- Physical examination;
- Record concomitant treatments;
- Record adverse events;
- Initiate chemotherapy cycle 4.

6.4.8. Phase 2 and Phase 2 Extension Week 11/Day 77 (only for patients in IMU-131 plus chemotherapy cohorts)

The visit window for Day 77 is +/- 7 days of the scheduled visit. Day 77 procedures should be performed in the following order:

- Weight, and vital signs (blood pressure, temperature and heart rate);
- Urine pregnancy test (female);
- Administer IMU-131 vaccination;
- Record body temperature 30 (+/-10) minutes after vaccination;
- Record concomitant treatments;
- Record adverse events.

6.4.9. Phase 2 and Phase 2 Extension Week 12/Day 84 (Repeat every 12 weeks/84 days)

The visit window for Day 84 is +/- 7 days of the scheduled visit. Day 84 procedures should be performed in the following order:

- Weight, and vital signs (blood pressure, temperature and heart rate);
- Blood sample for hematology and serum chemistry;
- Blood sample for humoral and cellular immunology;
- Blood sample for exploratory endpoints;
- Urine pregnancy test (female);
- Physical examination;
- ECOG performance score;

Investigational Product: IMU-131
Protocol Identifier: IMU.ACS.001
Protocol Version: Protocol Global Amendment #5, 27 September 2023

- Cardiac assessment by echocardiography or MUGA scan and 12-lead ECG;
- Radiographic assessment;
- Optional tumor biopsy sample (at Day 84);
- Record concomitant treatments;
- Record adverse events;
- Initiate chemotherapy cycle 5.

6.4.10. Phase 2 and Phase 2 Extension Week 15/Day 105

The visit window for Day 105 is +/- 7 days of the scheduled visit. Day 105 procedures should be performed in the following order:

- Blood sample for hematology and serum chemistry;
- Weight, and vital signs (blood pressure, temperature and heart rate);
- Urine pregnancy test (female);
- Physical examination;
- Record concomitant treatments;
- Record adverse events;
- Initiate chemotherapy cycle 6.

6.4.11. Phase 2 and Phase 2 Extension Week 18/Day 126 (Repeat every 12 weeks/84 days)

The visit window for Day 126 is +/- 7 days of the scheduled visit. Day 126 procedures should be performed in the following order:

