6.5. Patient Withdrawal

6.5.1. Main discontinuation criteria

Patients will discontinue study treatment and complete the study according to the study protocol when there is documented evidence of disease progression according to RECIST 1.1 response criteria or if unacceptable toxicity occurs. Patients may discontinue study treatment and be withdrawn from the study prematurely based on symptomatic clinical disease progression without documented radiographic evidence only after discussion with the Sponsor/medical monitor.

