8.11. Phase 2/Phase 2 Extension Unscheduled Visit

Unscheduled visits may be conducted at any time during Phase 2 by the investigator if clinically indicated for the care of the patient.

Investigational Product: IMU-131
Protocol Identifier: IMU.ACS.001
Protocol Version: Protocol Global Amendment #5, 27 September 2023

An unscheduled visit may include any of the protocol required assessments listed in [Section 8: Phase 2 Assessments](#). The exact assessments conducted at the unscheduled visit will be specified by the investigator and recorded in the CRF. Additional tests and procedures may be performed at the unscheduled visit for the clinical care of the patient after discussion with, and agreement of, the medical monitor.

8.12. Phase 2 Post-treatment Follow Up (FU) Visit (Every 42 days after EoT visit)

After disease progression, anti-cancer therapy and survival information will be collected every 6 weeks until death, withdrawal or end of trial. Anti-cancer therapy and survival information may be collected more frequently than every 6 weeks for quality control and data cleaning purposes. After discontinuation from the study for any reason other than disease progression, radiographic change will be collected every 6 weeks until determination of progressive disease.

All patients will be followed for radiographic change until determination of progressive disease and survival information and anti-cancer treatment until death, unless the patient requests to be withdrawn from radiographic change assessment and survival follow-up contact or the trial ends. Requests for withdrawal must be documented in the source documents and signed by the investigator.

Phase 2 extension patients will no longer complete Post-Treatment Follow Up visits.

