#### Treatment Period

Patient who are determined to be eligible for the study will be randomized on the Baseline/Day 0 visit. Treatment for both groups will begin at the Baseline/Day 0 visit.

Patients in the IMU-131 plus chemotherapy group will receive vaccination of IMU-131 at Baseline/Day 0, Day 14, Day 35, Day 77, Day 140 and then every 63 days until disease progression. Patients in both the IMU-131 plus chemotherapy group and the chemotherapy alone group will receive chemotherapy starting at the Baseline/Day 0 visit and then every 21 days for a maximum of 6 cycles as clinically indicated or until disease progression, whichever occurs sooner. Chemotherapy will be consisting of:

- Cisplatin by intravenous administration at 80 mg/m^2 on the first day of each cycle and either 5-FU, 4000 mg/m^2 CIV (administered as 1000 mg/m^2/day as continuous infusion for 96 hours on days 1 to 4 of each cycle) or capecitabine for 14 days at 2000 mg/m^2/day, orally (administered as 1000 mg/m^2 twice daily morning and evening for a total of 2000 mg/m^2/day on days 1 to 14 of each cycle);
- Or oxaliplatin, by intravenous administration at 130 mg/m^2 on Day 1 of each cycle and capecitabine for 14 days at 2000 mg/m^2/day, orally (administered as 1000 mg/m^2 twice daily morning and evening for a total of 2000 mg/m^2/day on days 1 to 14 of each cycle).

Patients who withdraw from the treatment or have progressive disease will undergo the End of Treatment (EoT) assessments as planned in the [Schedule of Study Procedures](#).

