## 8.2.8. Sensitivity Analysis

### 8.2.8.1. Clinical Disease Progression

Addition to original disease progression definition, clinical disease progression can be also considered as evidence of disease progression when there is no supportive radiographic assessment of PD. Clinical disease progression is “Progression Disease” leading to treatment discontinuation on eCRF end of treatment page identified by clinical assessment. The date of documented progression disease on eCRF end of treatment page will be used as the event date in a sensitivity analysis. The same full event and censoring rules show in [Table 8-1](#) will be implemented as well but including clinical disease progression as evidence of disease progression when there is no supportive radiographic assessment of PD.

[REDACTED]

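### After cycle 6, the PFS and TTP rule that censors stops for symptomatic deterioration applies mainly to the vaccine arm and may bias PFS towards IMU-131

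*SAP*

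**What the plan says.** - **Censoring row.** SAP Table 8-1 (PFS) has a row for "Treatment discontinuation due to symptomatic deterioration prior to disease progression". The outcome is censored, at the later of randomization and the last progression-free scan before the stop. Table 8-2 (TTP) repeats the row.
- **Length of treatment.** Under SAP 3.1 (Treatment Period) both arms start chemotherapy at Day 0, "then every 21 days for a maximum of 6 cycles as clinically indicated or until disease progression, whichever occurs sooner". Protocol 6.4.10 places "Initiate chemotherapy cycle 6" at Day 105. Only the vaccine arm also receives IMU-131, on Days 0, 14 and 35 and then on "Day 77, Day 140 and then every 63 days until disease progression".
- **End of treatment.** SAP 7.3.1 takes the later of the last injection (where there is one) and the last chemotherapy. In the control arm this can only be the last chemotherapy.
- **Stopping for symptoms.** Protocol 6.5.1: "Patients may discontinue study treatment and be withdrawn from the study prematurely based on symptomatic clinical disease progression without documented radiographic evidence". A discussion with the sponsor or medical monitor must come first. Under SAP 4.4 only the central image readers are blinded.
- **Follow-up.** Protocol 8.12 says that after discontinuation for a reason other than progression, "radiographic change will be collected every 6 weeks until determination of progressive disease". Survival is followed too.
- **Definition.** SAP 8.2.1 and Protocol 2.2 define PFS as the first of centrally read progression or death. The PFS censoring text in Protocol 10.7.2 has no symptomatic-deterioration rule.
- **Sensitivity analysis.** SAP 8.2.8.1 also counts clinical progression without a supporting scan, provided it is progression "leading to treatment discontinuation on eCRF end of treatment page identified by clinical assessment".

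**The concern.** The row is triggered by stopping study treatment, and the arms differ in how long there is treatment to stop. Patients who stop because they are deteriorating are likely to be close to progression or death, so censoring them is informative. If this happens in both arms alike, the comparison suffers little. If it happens mainly in the vaccine arm, likely events disappear from that arm and PFS favours IMU-131 even with no true effect.

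The stop is also a judgement made by staff who know the arm. The rule discards follow-up that the protocol sets out to collect, and it sits badly with the SAP's own definition of PFS. PFS has its own formal analysis at only 24 events, so a few patients matter.

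**Working it through.** The 24-event target cannot be re-derived, because the sample-size text is not in the public version. The point does not depend on it.

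**1. Timing.** Cycle k starts on Day 21 × (k − 1): Days 0, 21, 42, 63, 84 and 105. The last agrees with Protocol 6.4.10. Cycle 6 ends at 105 + 21 = Day 126. Vaccinations continue on Days 140, 203 (140 + 63), 266 and so on.

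**2. The same course in each arm.** As an illustration, take a clean scan on Day 126, deterioration on Day 150, and central progression at the next scan (126 + 42 = Day 168).
- Vaccine arm, stops IMU-131: censored at Day 126.
- Control arm, no study treatment left to stop: PFS event at Day 168.
- Control arm, starts new therapy before Day 168: censored at Day 126 under the subsequent-treatment row.

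**3. Patients affected.** Day 126 is 126 / 30.4375 = 4.14 months. With exponential PFS and median m months, the share still event-free is 0.5^(4.14/m): 49%, 59% and 66% for m = 4, 5.5 and 7. With 36 patients randomized 1:1, the expected number of vaccine patients censored by the row after Day 126 is 18 × q × that share, where q is the share of progressions that present first as deterioration. This runs from 18 × 0.10 × 0.49 = 0.9 to 18 × 0.30 × 0.66 = 3.6.

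**4. Size of the bias (simulation, true hazard ratio 1).**
- From the documents: scans every 42 days; the row operating in both arms to Day 126 and in the vaccine arm only afterwards.
- Assumed, not in the documents: exponential PFS with m = 4 to 7 months; q = 10 to 30%; r = share of off-treatment control patients with deterioration who are censored anyway for new therapy.

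Apparent PFS hazard ratio (vaccine/control), Cox model, 60,000 per arm:

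| m (months) | q | r = 0 | r = 50% | r = 100% |
|---|---|---|---|---|
| 4 | 10% | 0.96 | 0.99 | 0.99 |
| 4 | 20% | 0.91 | 0.96 | 1.00 |
| 4 | 30% | 0.86 | 0.92 | 1.00 |
| 5.5 | 10% | 0.94 | 0.97 | 1.00 |
| 5.5 | 20% | 0.89 | 0.94 | 1.00 |
| 5.5 | 30% | 0.82 | 0.91 | 1.00 |
| 7 | 10% | 0.94 | 0.97 | 0.99 |
| 7 | 20% | 0.87 | 0.93 | 0.99 |
| 7 | 30% | 0.80 | 0.89 | 1.01 |

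For scale, 24 events give a standard error for the log hazard ratio of about √(4/24) = 0.41. A bias to 0.96 is 0.04 / 0.41 = 0.1 standard errors, and a bias to 0.80 is 0.22 / 0.41 = 0.5.

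At an assumed one-sided 5% level (18 per arm, 1,500 runs, everyone followed to event or censoring), the false-positive rate is about 6.5-15% for r = 0, 5-10% for r = 50% and 5-7% for r = 100%.

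**5. Sensitivity analysis 8.2.8.1.** Same model, m = 5 to 7 months. The hazard ratio is about 1.00-1.03 for r = 0, 1.03-1.12 for r = 50%, and from 1.05 up to about 1.25 for r = 100%. In the first case it restores the vaccine events that the main rule removed. In the others, control patients censored for new therapy have no matching clinical-progression event, because that event also requires stopping study treatment.

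**6. Row removed.** With both arms followed to progression or death, the simulated hazard ratio is 1.005.

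**The case against.** **The new-therapy row may restore balance.** This stands as a limit on size. If nearly all deteriorating control patients start other treatment before progression, the bias vanishes; if half do, it shrinks. Nothing in the documents settles the share.

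**A control patient could still be recorded as a symptomatic stop.** The end-of-treatment visit is triggered by progression or withdrawal in both arms, so a control patient past cycle 6 still reaches that page. What the page allows is not visible. Even so, balance need not return. If the stop is dated at the last chemotherapy, as SAP 7.3.1 suggests, the control patient is censored back to about Day 84-126. A simulation of that reading gave apparent hazard ratios of 0.79-0.97 over the same values of q.

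**Day 126 is not a hard limit.** Correct. Chemotherapy may be delayed, and before cycle 6 ends the row can apply in both arms. The imbalance is therefore partial, not absolute.

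**Some vaccine patients may count as events after all.** Table 8-1 gives no order of precedence. A patient who stops for deterioration and dies within 98 days of the last clean scan fits both an event row and this censoring row. That tempers the size and is a gap in its own right.

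**The inputs are assumed.** Also correct. Progression by RECIST is the default reason for stopping, symptomatic stops need prior discussion, and q may be small.

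A reader might infer that PFS is shown to be biased, or that neither the main analysis nor 8.2.8.1 can be relied on. The documents support neither. The bias depends on quantities they do not give, and at r = 0 or r = 100% one of the two analyses is close to unbiased.

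**Conclusion.** The point holds as a risk, not as a demonstrated bias. On the literal text, the symptomatic-deterioration row applies unequally between the arms after cycle 6, and where that matters the direction favours IMU-131. The ranges in the table rest wholly on the assumed median, q and r, and the low end is a worst case in which no control patient is censored for new therapy.

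TTP is probably affected less, because Table 8-2 censors deaths in both arms and only later progression scans are lost; this was not simulated. OS is untouched, and SAP 12 says that missing the PFS criterion does not block the survival analysis. Section 8.2.8.1 is a useful partial check, but its own dependence on stopping treatment means that it can err in the other direction.

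This should be fixed, because PFS is formally analysed on few events and the repair is cheap. It does not threaten the primary conclusion.

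**What to change.** 1. Delete the symptomatic-deterioration row from Tables 8-1 and 8-2, and the mention of it in the row for patients with no event and no new therapy.
2. For these patients count the next centrally read progression (and, for PFS, death) from the scheduled follow-up, under the same interval rules in both arms.
3. State the order of precedence of the remaining rows.
4. In 8.2.8.1, define clinical progression independently of being on study treatment, so far as the data collected allow.
5. Report the number of patients censored by each row and arm. The new-therapy row remains, and this shows whether it falls evenly.

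The cost is SAP wording and reprogramming of two tables; the main change needs no new data. The downside is that some events will be dated at a later scan or at death. The change also relies on the post-discontinuation scans having been done: a death more than 98 days after the last clean scan would still be censored.

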### 8.2.2. Time to Progression (TTP)

The time to progression is defined as the time from randomization to the disease progression on or prior to the clinical cutoff date.

Similar with PFS, the calculation of TTP is a two steps process.

- Determination of date of disease progression, which is the date of assessment corresponding to the first date time that overall tumor response is “Progressive Disease” on the Overall Tumor Response-RECIST eCRF
- Calculation of duration from randomization to disease progression, or censoring date as described in [Table 8-2](#) as follows. In cases where a patient’s tumor is downstaged to become surgically resectable, this is considered a response to treatment with subsequent surgery being part of the patient’s normal clinical care. Such cases are considered evaluable for progression analysis at time of confirmed progressive disease.

[figure not shown]
**Table 8-2 Censoring Conventions for TTP**

Situation	Date of Progression or Censoring	Outcome
Disease progression, and time interval between progression date and previous tumor assessment date with progression-free response is less than or equal to 98 days	Earliest of: 

• Date of first tumor assessment showing new lesion

• Date of first tumor assessment with overall response of PD

	Event
Disease progression, and time interval between the progression date and the previous tumor assessment date with progression-free response is greater than 98 days.	Latest of: 

• the last progression-free assessment date

• randomization date

	Censored
Death without any post-baseline radiological assessment, and time interval between death date and randomization date is less than or equal to 98 days	Death date	Censored
Death without any post-baseline radiological assessment, and time interval between death date and randomization date is greater than 98 days	Randomization date	Censored

Death before documented progression, and time interval between death date and previous tumor assessment date with progression-free response is less than or equal to 98 days	Death date	Censored
Death before documented progression, and time interval between death date and previous tumor assessment date with progression-free response is greater than 98 days	The last progression-free assessment date	Censored
No death or disease progression, no treatment discontinuation due to symptomatic deterioration, and no subsequent anti-cancer therapy (i.e., systemic anti-cancer therapy, anti-cancer surgery, curative radiotherapy).	Latest of 

the last progression-free assessment date

randomization date

	Censored
Subsequent anti-cancer treatment (i.e., systemic anti-cancer therapy, anti-cancer surgery, radiotherapy) started prior to progression	Latest of 

the last progression-free assessment date prior to start of anti-cancer treatment

randomization date

	Censored
Treatment discontinuation due to symptomatic deterioration prior to disease progression	Latest of 

the last progression-free assessment date before treatment discontinuation date

randomization date

	Censored

Time to Progression is calculated as follows.

TPP = Analysis date defined above – randomization date + 1

### 8.2.3. Disease Control Rate (DCR)

The best overall response (BOR) for each patient will be derived based on blinded central review disease response assessments according to RECIST 1.1, using all the assessments from randomization until the data cutoff date or the end of study. If there is no post randomization

disease assessment, the BOR will be “No Post Randomization Assessment”; and if all the post randomization tumor responses are not evaluable, the BOR will be “Not Evaluable” (NE).

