- B A 1 x 10 mL whole blood sample to assess vaccine-specific cytokine levels and in-vitro inhibition of tumor cell growth will be obtained from each patient at Days 0, 84 then every 84 days and at EoT visit.

Investigational Product: IMU-131
Protocol Identifier: IMU.ACS.001
Protocol Version: Protocol Global Amendment #5, 27 September 2023

- C 1 x 10 mL (i.e. 1 tube) whole blood sample for humoral immunity at Baseline, Days 21, 42, 63, 84, 126 then every 42 days and EoT visit and 40 mL blood sample at Screening (Phase 2 Extension only), Baseline, Days 84 then every 84 days and EoT visit for cellular immunity. To be taken prior to vaccination at Baseline visit.
- D Chemotherapy will be administered as a concomitant therapy to all patients as a 21-day regimen consisting of: cisplatin by intravenous administration at 80 mg/m² on the first day of each cycle and either 5-FU, 4000 mg/m² CIV (administered as 1000 mg/m²/day as continuous infusion for 96 hours on days 1 to 4 of each cycle) or capecitabine for 14 days at 2000 mg/m²/day, orally (administered as 1000 mg/m² twice daily morning and evening for a total of 2000 mg/m²/day on days 1 to 14 of each cycle), or capecitabine for 14 days at 2000 mg/m²/day, orally (administered as 1000 mg/m² twice daily morning and evening for a total of 2000 mg/m²/day on days 1 to 14 of each cycle) and oxaliplatin, by intravenous administration at 130 mg/m² on Day 1 of each cycle. Body weight to be measured and body surface area to be calculated based on weight and baseline height at the start of each 21-day chemotherapy cycle. Chemotherapy continues until ceased by the investigator as clinically indicated for the care of the patient. To document compliance while away from the clinic, patients will record capecitabine treatment in a patient diary.
- E Radiographic assessment to occur within 14 days prior to Baseline Visit, then at Days 42, 84, 126 every 42 days thereafter. Radiographic assessment continues until disease progression according to RECIST 1.1 response criteria, withdrawal or end of trial.
- F Chemotherapy continues for up to 6 cycles until disease progression or until ceased by the investigator as clinically indicated for the care of the patient, whichever occurs first.
- G Radiographic assessment according to RECIST 1.1 response criteria at post-treatment follow-up visit only for patients who have ended study treatment prior to disease progression.

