#### Secondary Efficacy Endpoints

- PFS measured from randomization to date of earliest progressive disease (PD) based on blinded central review according to RECIST 1.1 criteria, or to date of death from any cause
- TTP measured from randomization to date of earliest PD based on blinded central review according to RECIST 1.1 criteria
- ORR measured from randomization as the proportion of patients achieving a best overall response of CR or PR based on blinded central review according to RECIST 1.1 criteria
- DCR measured from randomization as the proportion of patients achieving a best overall response of complete response (CR), partial response (PR) or stable disease (SD) based on blinded central review according to RECIST 1.1 criteria
- DOR measure from when earliest CR or PR is observed to PD or death due to any cause based on blinded central review according to RECIST 1.1 criteria
- Percentage CTS measured from baseline as the sum of diameters based on blinded central review according to RECIST 1.1 criteria

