## 8. Efficacy Analyses

All imaging will be assessed by both investigators and a blinded central radiography review vendor, according to Response Evaluation Criteria In Solid Tumors version 1.1 (RECIST 1.1). The blinded central review disease response assessments will be used as the primary measure for the efficacy endpoints, and the investigator disease assessments will be used as supportive measures for these analyses. All the disease assessments from the randomization until the clinical cutoff date or the end of study will be used in the deviation of the secondary efficacy endpoints, unless otherwise specified.

[figure not shown]

For all the time-to-event endpoints described in this section, the time interval will be reported in unit of week.

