#### **8.2.4. Objective Response Rate (ORR)**

ORR is defined as the proportion of patients with a BOR of CR or PR after randomization.

[figure not shown]

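### Best overall response has no visible stop at subsequent anti-cancer therapy, so a CR or PR first reached on new treatment started before PD would count in ORR and DOR, although PFS and TTP are censored before that treatment

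*SAP*

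**What the plan says.** **Response endpoints.** SAP 8.2.3 derives BOR for each patient from the blinded central review under RECIST 1.1, "using all the assessments from randomization until the data cutoff date or the end of study". The opening of SAP 8 sets the same window for the secondary endpoints generally: "All the disease assessments from the randomization until the clinical cutoff date or the end of study will be used", save where the SAP specifies something else. SAP 8.2.4 builds on this: "ORR is defined as the proportion of patients with a BOR of CR or PR after randomization". DCR (SAP 3.2) counts SD as well. DOR (SAP 8.2.5) runs from the first CR or PR to PD or death, with censoring at the last adequate assessment. It refers back to 8.2.1 only for the definitions of progression and of an adequate assessment, and it does not mention new therapy. SAP 8.2.6 carries the same methods into the investigator-assessed analyses.

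**Progression endpoints.** Table 8-1 has a row for "Subsequent anti-cancer treatment (i.e., systemic anti-cancer therapy, anti-cancer surgery, radiotherapy) started prior to progression". The outcome is censoring, at the later of randomization and "the last progression-free assessment date prior to start of anti-cancer treatment". Table 8-2 repeats this for TTP.

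**Imaging.** Under Protocol 8.12, after a patient leaves the study for a reason other than progression, "radiographic change will be collected every 6 weeks until determination of progressive disease". Footnote G of Protocol Table 3 says that post-treatment scans are "only for patients who have ended study treatment prior to disease progression". Subsequent anti-cancer treatment is recorded at the same visits (Protocol 6.4.14), and SAP 8 sends all imaging to central review.

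**The concern.** The SAP treats the start of new therapy as the end of informative follow-up for PFS and TTP, but not for response. A patient could stop study treatment without PD, start something else, respond to it, and be tabulated as a responder to the randomized regimen. Blinded reading does not prevent this, because the response is real and only its attribution is wrong.

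The situation is foreseeable. Table 8-1 gives it a row, and Protocol 6.5.1 allows withdrawal for symptomatic progression without radiographic evidence. Switching may also differ by arm. The trial is open-label, and chemotherapy ends after at most 6 cycles in both arms while vaccination continues to progression in one. Control patients without PD then have no study treatment, so early switching could be more common among them and raise the control ORR. The opposite is also possible, so the direction of any bias is unknown.

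**Working it through.** The documents give no ORR or DCR figure to reproduce. The check is a comparison of rules followed by a scale calculation.

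**1. One hypothetical patient under each rule.** Randomized on Day 0. SD at the Day 42 scan. Stops treatment without PD and starts new systemic therapy between Days 42 and 84. PR at Day 84, PD at Day 126.

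| Endpoint | Rule | Result |
|---|---|---|
| PFS, TTP | Tables 8-1, 8-2 | Censored at Day 42; 42 − 0 + 1 = 43 days |
| ORR | 8.2.3, 8.2.4 | BOR = PR: success |
| DCR | 3.2, 8.2.3 | Success, but already so from the Day 42 SD |
| DOR | 8.2.5 | Starts Day 84, event Day 126; 126 − 84 = 42 days |

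The whole DOR interval lies after the date at which PFS stopped counting. DCR is unchanged; it would change only if the patient had no evaluable non-PD scan before the switch.

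**2. Scale.** Inputs: 36 patients (SAP 3.1) and 1:1 allocation (SAP 4.4), so 36/2 = 18 per arm.

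- One misattributed response: 1/18 = 5.6 points on that arm's ORR.
- Yardstick: the phase 3 trastuzumab trial described in Protocol 1.2 had response rates of 47.3% and 34.5%. The difference is 12.8 points, and 0.128 × 18 = 2.3 patients.

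**3. Sensitivity range.** The number k of affected patients is not in the documents. Assume k = 0 to 4, all in one arm, and 6/18 true responders in each arm (0.345 × 18 = 6.2, rounded to 6).

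| k | Affected arm | Other arm | Spurious difference | Fisher p |
|---|---|---|---|---|
| 0 | 6/18 = 33.3% | 33.3% | 0 | 1.00 |
| 1 | 7/18 = 38.9% | 33.3% | 5.6 points | 1.00 |
| 2 | 8/18 = 44.4% | 33.3% | 11.1 points | 0.73 |
| 3 | 9/18 = 50.0% | 33.3% | 16.7 points | 0.50 |
| 4 | 10/18 = 55.6% | 33.3% | 22.2 points | 0.32 |

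**4. Can it produce significance?** Power for 34.5% vs 47.3% with 18 per arm, two-sided 5%, normal approximation:

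- SE under the null = √(2 × 0.409 × 0.591/18) = 0.164
- SE under the alternative = √((0.345 × 0.655 + 0.473 × 0.527)/18) = 0.162
- Power = Φ((0.128 − 1.96 × 0.164)/0.162) = Φ(−1.19), about 12%

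The ORR comparison has little power at that difference, and even k = 4 leaves p = 0.32.

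**The case against.** **The public copy is incomplete.** The general window in SAP 8 allows exceptions, 8.2.3 shows no DCR analysis text, and 8.2.4 ends in a missing block. A restriction could sit there. This stands as a caveat, but such a restriction would contradict the visible instruction in 8.2.3 to use all assessments. BOR is also tied to RECIST 1.1; whether that standard limits the assessments cannot be checked from these documents, so the SAP should say so itself.

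**The affected group is narrow.** A reader might infer that ordinary second-line responses after PD are counted. The documents do not support that: post-treatment scans are scheduled only for patients who ended treatment before PD. Leaving for clinical progression needs discussion with the sponsor or medical monitor (Protocol 6.5.1). Footnote E of Protocol Table 3 also lets withdrawal end imaging, whereas the SAP's footnote E continues it. The group may be empty.

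**Counting response whatever therapy follows is a legitimate treatment-policy choice.** This is fair: endpoints may treat new therapy differently, so the mismatch with PFS is not an error in itself. But the SAP does not state that choice, and keeping the all-assessments version as a sensitivity analysis preserves it.

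**A cut at every therapy listed in Table 8-1 would create a new conflict.** This stands. SAP 8.2.1 and 8.2.2 treat surgery after downstaging as normal care following a response and take the event at later confirmed PD. The same tables list anti-cancer surgery as a reason to censor.

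**Conclusion.** On the visible text the concern holds for ORR and DOR. Following the SAP as written could credit a response on new therapy, started before PD, to the randomized arm. Each such patient moves an arm's ORR by 5.6 points, and two or three in one arm would create or hide a difference about as large as the trastuzumab benchmark. That range is illustrative and rests on 18 patients per arm and an assumed number of switchers.

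Several stronger readings are tempting and not supported:

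- That DCR is equally affected. It is not, because SD before the switch is already a success.
- That a false significant result is likely. The range above gives p = 0.32 at its extreme.
- That the vaccine arm is favoured. The direction is unknown.
- That CTS shares the fault. SAP 8.2.7 is redacted, so nothing can be said about it.
- That the main trial conclusion is at risk. OS does not use BOR, and PFS and TTP already censor before new therapy.

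Requiring confirmed responses, as the protocol's endpoint definitions do and the SAP's do not, would not by itself remove a response to later therapy.

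**What to change.** - In SAP 8 and 8.2.3, for the main ORR and DCR analyses, derive BOR from assessments up to the earliest of first PD, start of subsequent anti-cancer therapy, or cutoff.
- In SAP 8.2.5, censor DOR at the last adequate assessment before such therapy.
- State that surgery after downstaging is handled as in 8.2.1 and 8.2.2, and reconcile those sections with the anti-cancer surgery entry in Tables 8-1 and 8-2.
- Keep the all-assessments BOR as a sensitivity analysis.

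The cost is a few sentences, one filter on therapy dates that are already collected, one extra set of response tables, and a decision on the surgery wording. SAP 1 already provides for a final SAP amendment for significant changes between the PFS analysis and final lock. The downside is that a response first seen after an early switch is not counted in the main ORR; the sensitivity analysis still shows it.
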